## 10. Ethical Issues

### e. Risks

**Treatment:** Some risks are associated with the administration of psychosocial treatment. The primary risk is the evocation of uncomfortable levels of anxiety or other emotions during the treatment sessions. Some participants may find sessions stressful and react to them with anxiety.

**Recording:** Some participants may feel uncomfortable about the assessment and treatment sessions being recorded. However, this will be a required procedure. The purpose of the recording will be explained, confidentiality will be respected, and both informed consent and authorization for recording will be obtained as per requirements put forth by the Healthcare Information Portability and Accountability Act (HIPAA). Recordings will be marked only by subject identification codes and stored in password protected computer server accessible only to staff directly involved with the project.

**Self-Report Measures and Assessor Ratings:** No risks are seen associated with these assessment procedures other than discomfort associated with the audio-recording. These will be handled as described above for recording of assessment and therapy sessions.

## **2. ADEQUACY OF PROTECTION AGAINST RISKS**

### **a. Recruitment and Consent Procedures**

Following the recruitment procedures used in our past clinical treatment studies for PTSD with veterans, we used a variety of recruitment strategies (e.g., posting fliers throughout the medical center, clinic referrals). We will also create a study brochure for clinicians to provide to potential veteran participants. Based on past experiences, we anticipate clinic referrals to be the most effective recruitment strategy. The study announcements and brochure will state that the treatment is part of a research study that is available to qualified veterans. Interested veterans will be instructed to call for further information.

In accordance with HIPAA regulations, written informed consent will be obtained from each veteran after a thorough explanation of procedures by a project staff person and the opportunity for the veteran to ask and receive answers to questions. Veteran participants will be informed of the nature of the investigation, the types of assessments and treatments involved, alternative treatments, and the potential risks involved in participation and will be asked to sign an informed consent statement prior to participating in the proposed study. In addition, the participant will receive an explanation of how information related to their case will be handled including all parties involved, data management, and plans to publish data in group format without identifying information.

Veteran participants will also be informed that confidentiality may be broken under the following circumstances: disclosure of suicidal or homicidal intentions, disclosure of child abuse, disclosure of elder abuse. Confidentiality may be broken in such instances in order for protective measures to be taken.

### **b. Protection against risk**

1. We will carefully screen to identify individuals whose risk for potential adverse outcomes is elevated were they to participate in the proposed research. Such individuals will be excluded from the study. As an example, a person deemed high suicidal risk would be excluded from study participation. These individuals will be followed by study personnel (if they give consent to be followed).
2. Clinical staff will be trained to cope with any anxiety/distress experienced by participants during the assessments and treatment.
3. Careful monitoring of participants during the initial assessment and throughout the study will be conducted by the project staff. Participants will complete the PCL-5 at each assessment and treatment session in order to monitor symptoms (and potential symptom increases). Each participant will see the same clinician for each of their treatment visits and the same assessor for each assessment occasion. Following the clinical trial policy of the VA Boston Healthcare System

(VABHS) all participants will be given an emergency number to call after business hours in case of an emergency. This number will be the psychiatry on call system of the respective VA site.

4. Participants will be instructed to contact study personnel at any time (including during the follow-up period) in the event of worsening of symptoms or relapse. Participants whose clinical condition has substantially deteriorated will be removed from study treatment and appropriate clinical referrals will be made. These veterans will also be followed by study personnel, if they give permission to be followed.
5. Participants failing to benefit from the study treatments will be provided with appropriate clinical referrals. Participants who begin treatment and experience adverse outcomes related to the treatment being received will also be provided with appropriate clinical referrals. The appropriate clinical referrals will be determined by the judgment of clinicians and supervising staff familiar with the specific participant and may include cognitive-behavioral treatment, other psychotherapy, or referral for medication treatment.
6. As in any type of treatment or clinical research program, participants' confidentiality must be carefully guarded and respected. All data with identifying information will be stored in locked files or password-protected computer server. Data being analyzed will be identified by subject codes, and identifying information will be removed. The identity of participants will not be revealed in the presentation or publication of any results from the project. All personnel working on the project will be educated about the importance of strictly respecting participants' rights to confidentiality and will have completed several training courses including proper practice in accordance with HIPAA regulations, protection of human subjects, and computer security.
7. If new information emerges for one or both of the treatments in the study that indicates the treatment is associated with detrimental effects, we will alert participants of this new information and consult with IRB regarding whether or not the study should be stopped given the new information.

f. Potential Benefits

The direct benefit to veterans who enter this study will be to obtain relief from anxiety symptoms, decreased avoidance, decreased disability, and increased quality of life. For many individuals with PTSD the disorder has greatly impeded their social, vocational, and academic functioning among those veterans who are enrolled in college courses. The treatments offered in the study are recommended treatment approaches according to the VA/DoD clinical practice guidelines (2017). Thus, the treatments have strong evidence to support their effectiveness.

More broadly, establishing cost-effective, brief and readily deliverable alternatives to traditional (time intensive) psychotherapy options for veterans with PTSD has broad health and policy implications for the Department of Veteran Affairs given the high prevalence of this debilitating disorder in the veteran population.

3.

g. Analysis of Risks in Relation to Benefits

The risks in the study are low given that the treatments included are first line, recommended PTSD treatments, as outline in the VA/DoD Clinical Practice Guidelines. Moreover, veterans will be receiving high quality PTSD treatment with close supervision monitoring of the therapists, in

combination with greater attention (e.g., calling between sessions or when a session is missed) that is typically possible in routine clinical care. The study anticipates that veterans will reap treatment gain for both treatment conditions in the study. Thus, the potential benefit to the veteran is significant reduction of PTSD symptoms and improvement in quality of life. Overall, the risks to benefit ratio is very favorable.

#### **h. Stopping Rules**

A participant may always withdraw their participation at any time.

- A participant will be withdrawn from the study if:
  - They report a substantial increase in PTSD symptoms that is stable for 3 weeks and the participant indicates the increase is the result or likely the result of treatment they are receiving in the study.
  - The participant becomes high risk for suicide and is hospitalized.
  - The participant requires treatment (detox or residential) due to the substance use.
  - The participant becomes verbally or physically aggressive towards research staff.

4.

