To monitor suicide risk throughout the treatment phase, we will administer the BDI-II at each treatment session. If a participant endorses suicidal ideation at any level in response to question #9 (suicidal thoughts or wishes), a licensed psychologist will administer the MINI suicidal module. Participants deemed to be a high risk for suicide on the MINI (i.e., score of 17 or higher) will be removed from the study treatment and appropriate actions will be taken. These actions are described below in the data monitoring section. In addition, if the participant is willing, they will continue to be followed by the PI.

Homicidal risk will be assessed using approach recommended by *VA/DOD Clinical Practice Guideline for Major Depressive Disorder* (2009). At the initial assessment and at the beginning of each treatment session, participants will be directly asked whether they have thoughts of harming anyone. If the participant indicates they do have thoughts of harming someone, then the clinician will ask whether the participant has an active plan or method to harm someone (e.g., weapon in their home) and whom the participant wishes to harm. Further assessment will take place for participants who indicate that they have an active plan or method. Specifically, they will be asked whether they have ever lost control and acted violently and, if so, the severity of reported past violent behavior will be assessed. If a participant indicates that they have thoughts of harming someone and they have an active plan, the participant will be considered potentially high risk and further assessment will be conducted, as described in the section on managing adverse events.

We will monitor for a substantial increase in PTSD symptom severity during the treatment phase using the Posttraumatic Check List for DSM-5 (PCL-5). The PCL-5 is a 20 item self-report measure

of PTSD symptom severity. This measure will be completed at each assessment session and each treatment session. A substantial increase in symptoms is defined as at least 10-point increase in PTSD from the initial assessment and has been sustained for a three-week period (e.g., Foa et al., 2002).

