In the event that a participant experiences an increase in PTSD symptom severity but without suicidal/homicidal risk, the PI or site PI will intervene by asking direct questions about the nature and causes of the distress, conduct a PTSD assessment, and schedule extra contacts (assessments) if deemed necessary. Such individuals will be withdrawn from study treatment from the protocol if they report a substantial increase in the PTSD symptom severity (i.e. at least 10 points higher than their baseline PTSD symptom severity score) that is sustained over a three-week period and the cause of the increase is determined to be related to the study treatment. We have selected

the 10-point increase and 3-week time frame based on Foa, Zoellner et al. (2002) in which they emphasize the importance of using a reliable index score when considering increases (and decreases) in PTSD symptoms. Importantly, Foa and colleagues (2002) have reported that only a minority of participants showed an acute substantial increase in PTSD symptom severity during Prolonged Exposure treatment, and that this acute increase was not associated with an increased risk for dropout or poor treatment outcome. Nevertheless, to protect against risk, we will monitor participants for undue distress reactions and will use a 10-point increase from baseline assessment of PTSD symptom severity that is sustained for 3 weeks as a guide for potentially withdrawing a participant from the study treatment. If a participant is withdrawn from the study treatment, they will be followed by study personnel, if they agree to be followed, to ensure that they have received adequate clinical care. In addition, if they agree, the study will continue to conduct assessments with the participant. In addition, participants who are deemed ineligible to enroll in the trial will be referred to the appropriate VA mental health clinic. The PI or site PI will subsequently contact (within one week) these veterans to make sure that they have not experienced any barriers in following through with clinical referrals.

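### Section 10.h removes participants from the study, while the adverse-event procedure for the same PTSD worsening stops only study treatment and keeps assessing

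*Combined protocol and SAP*

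**What the plan says.** Section 10.h, Stopping Rules, begins "A participant will be withdrawn from the study if" and lists four triggers:

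1. a substantial PTSD increase, stable for 3 weeks, where "the participant indicates the increase is the result or likely the result of treatment they are receiving in the study";
2. high suicide risk with hospitalisation;
3. a need for detox or residential care because of substance use;
4. verbal or physical aggression towards research staff.

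It does not mention outcome assessments after withdrawal.

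Section 11, Protocol for Managing Adverse Events, covers the first event in more detail (at least 10 points above baseline, sustained for three weeks, related to treatment): "Such individuals will be withdrawn from study treatment from the protocol if they report a substantial increase in the PTSD symptom severity". It then adds: "In addition, if they agree, the study will continue to conduct assessments with the participant".

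Other places bear on the same question:

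- Section 10, Protection against risk, item 4: participants who have deteriorated substantially come off study treatment and are followed with permission.
- Section 11, Protocol for Monitoring Adverse Events: participants at high suicide risk (MINI score of 17 or more) "will be removed from the study treatment and appropriate actions will be taken", followed by "In addition, if the participant is willing, they will continue to be followed by the PI".
- Section 7, Assessment Schedule: anyone not attending all sessions is a treatment dropout, and dropouts are asked to complete every assessment.
- Section 9: active follow-up of those who leave, and a primary analysis of all randomised patients under missing at random (MAR).

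**The concern.** Two rules for one event prescribe different things. Under 10.h the person leaves the study; under the adverse-event procedure the person stops treatment and stays under assessment. Staff at three sites need one answer.

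The statistical stake is the primary outcome. CAPS-5 is scheduled at baseline and at 10, 20 and 30 weeks. A participant taken out of the study before week 10 contributes only the baseline score, and one taken out between weeks 10 and 20 loses the last two. The triggers select people likely to be doing badly. The primary analysis would still include them, but their follow-up would rest entirely on MAR, which is least secure when the removal rule is itself tied to a bad course. If more such people were removed from one arm than from the other, the treatment difference would move.

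**Working it through.** **Step 1. The texts by trigger**

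| Trigger in 10.h | 10.h consequence | Elsewhere | Relation |
|---|---|---|---|
| Treatment-attributed PTSD worsening, 3 weeks | Out of the study | Managing Adverse Events: off study treatment, assessments continue if the participant agrees. Section 10 item 4: off study treatment, followed with permission | Contradiction on scope |
| High suicide risk and hospitalised | Out of the study | Monitoring Adverse Events: off study treatment at MINI 17 or more, investigator follow-up if willing | Out of line; 10.h describes a narrower event, and the other text does not mention outcome assessments |
| Detox or residential care | Out of the study | No trigger-specific rule; general dropout rules in Sections 7 and 9 | 10.h is the only specific rule |
| Aggression towards staff | Out of the study | No trigger-specific rule; general dropout rules in Sections 7 and 9 | 10.h is the only specific rule |

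The detox trigger can occur, because Section 7 excludes only severe substance use disorder. No section states an order of precedence.

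**Step 2. Size, as an illustration**

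Documented inputs: 90 per arm; margin 10 CAPS-5 points; the whole 95% confidence interval must lie below 10. The plan gives no SD, power calculation, attrition rate or trigger rate, so there is no figure of its own to reproduce. Everything below that is marked assumed is mine.

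*Shift in the estimate.* Let k be the net excess of participants lost in one arm (assumed 1 to 5) and gap the amount by which their true CAPS-5 is worse than MAR predicts (assumed 10 or 20). Then shift = k × gap / 90.

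| gap | k = 1 | k = 3 | k = 5 |
|---|---|---|---|
| 10 | 0.11 | 0.33 | 0.56 |
| 20 | 0.22 | 0.67 | 1.11 |

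This is 1.1% to 11.1% of the margin. A 1-point shift needs k = 90/10 = 9, or 90/20 = 4.5, about 5. The shift in WET minus PE is negative (favours WET) if the excess loss is in WET and positive if it is in PE. It is zero if losses and gaps are equal.

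*Effect on the decision, assumed SD 13.* SE = 13 × √(2/90) = 1.938. Half-width = 1.96 × 1.938 = 3.80. Non-inferiority is declared if the estimate is below 10 − 3.80 = 6.20, so P = Φ((6.20 − true difference − shift)/1.938).

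| True difference (assumed) | shift −1.11 | 0 | +1.11 |
|---|---|---|---|
| 0 | 0.9999 | 0.9993 | 0.9957 |
| 3 | 0.987 | 0.951 | 0.860 |
| 10 (error rate at the margin) | 0.083 | 0.025 | 0.006 |

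At true difference 0, the same formula gives above 0.999 throughout for SD 10; 0.999, 0.994 and 0.978 for SD 15; and 0.961, 0.918 and 0.847 for SD 20 (SE 2.981, threshold 4.16).

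*Precision alone.* Equal loss of 1%, 2%, 5% or 10% per arm (assumed) leaves about 89, 88, 86 or 81. The SE rises by the factor 1/√(1 − loss), that is by 0.5%, 1.0%, 2.6% or 5.4%. At SD 20 and true difference 0, power goes from 0.918 to 0.916, 0.913, 0.905 or 0.889.

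**The case against.** The strongest reply is that the plan already answers this. Anyone stopped in mid-treatment under any of the four triggers fits the Section 7 definition of a treatment dropout and is to be asked for all assessments. Section 9 promises follow-up whatever the reason for leaving. Section 10 item 4 and both Section 11 procedures stop treatment only. On that view 10.h is a loosely worded list and nobody intends to stop collecting CAPS-5.

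As evidence of intent this stands, and it limits the likely harm. It does not remove the conflict. Dropping out can be read as the participant's own decision, whereas 10.h is a mandatory removal by the study. The Section 7 definition does not reach a trigger that occurs after treatment is complete. No text says that the general rule overrides the specific one.

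A reader might also infer that the two sections conflict on who attributes the worsening to treatment and on how binding the rule is. The documents do not support that:

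- **Attribution.** Managing Adverse Events requires that "the cause of the increase is determined to be related to the study treatment", and just before that it has the lead or site investigator asking about causes. The decider is therefore implied, and the participant's own view in 10.h is a natural input.
- **Force.** The softer phrase "as a guide for potentially withdrawing a participant from the study treatment" is in tension with the mandatory wording in the same section. It is not a conflict created by 10.h.
- **Definition.** Monitoring Adverse Events already defines a substantial increase, so 10.h does not lack a threshold.

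**Conclusion.** The concern holds as a contradiction of scope for treatment-attributed PTSD worsening, and as an unsupported exit from the study for detox or residential care and for aggression. The text mismatch is certain. Loss of outcomes depends on staff following 10.h literally and is zero if Sections 7, 9 and 11 are followed.

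Size and direction cannot be estimated from the documents. Under the assumed inputs the shift is at most 1.11 points, small against the 10-point margin, and with a true difference of 0 it barely alters the chance of showing non-inferiority at SD 10 to 15. It matters more at SD 20, or when the true difference is well above 0, and those cases rest equally on assumption.

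Two stronger readings should be resisted. One is that 10.h biases the trial towards or against WET. PE has more sessions and so more occasions to trigger a rule, but no rates by arm are given. The other is that all four events are rare. Section 11 calls suicidal and homicidal ideation and increases in PTSD and depression symptoms unlikely in response to treatment. It says nothing about the frequency of detox, residential care or aggression.

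This should be fixed because a removal rule that touches the primary outcome ought to be unambiguous and the correction is nearly free. It does not show that the result is compromised.

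**What to change.** In Section 10.h, replace withdrawal from the study with withdrawal from study treatment, and keep all four triggers. Add that the 10-, 20- and 30-week assessments continue for everyone who agrees, by telephone where needed, with discretion to end contact where staff safety requires it. For the worsening trigger, cross-refer to Protocol for Managing Adverse Events so that one rule governs.

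The cost is protocol wording. Sections 7 and 8 already provide centralised telephone assessment, and the few extra interviews are ones already planned for every randomised participant.

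### The stopping rule for sustained PTSD worsening ends study participation, while the adverse-event section ends only study treatment and keeps assessing; the two should be aligned

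*Combined protocol and SAP*

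**What the plan says.** Two places in the combined protocol and SAP say what happens to a participant whose PTSD symptoms rise and stay up.

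- **Section 10, h. Stopping Rules.** The list opens "A participant will be withdrawn from the study if". Its first trigger reads "They report a substantial increase in PTSD symptoms that is stable for 3 weeks and the participant indicates the increase is the result", or the likely result, of study treatment. Three further triggers share the same opening: hospitalisation for high suicide risk, a need for detox or residential substance-use treatment, and aggression towards staff. Later assessments are not mentioned.
- **Section 11, Protocol for Managing Adverse Events.** "Such individuals will be withdrawn from study treatment from the protocol if they report a substantial increase in the PTSD symptom severity", of at least 10 points over baseline for three weeks, provided that "the cause of the increase is determined to be related to the study treatment". The same paragraph later describes the threshold "as a guide for potentially withdrawing a participant from the study treatment", and says that "if they agree, the study will continue to conduct assessments with the participant".

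Four other places bear on the question.

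- **Section 10, Protection against risk, item 4:** "Participants whose clinical condition has substantially deteriorated will be removed from study treatment and appropriate clinical referrals will be made". Study personnel then follow these veterans if they permit it.
- **Section 11, Protocol for Monitoring Adverse Events:** participants at high suicide risk "will be removed from the study treatment and appropriate actions will be taken", and the PI continues to follow those who are willing.
- **Section 7, Assessment Schedule:** a treatment dropout is anyone who does not attend every session, and dropouts are asked to complete all assessments.
- **Section 9, Statistical Analysis Plan:** follow-up is pursued whatever the reason for dropping out. Missing data are handled by direct maximum likelihood or multiple imputation, assuming data are missing at random.

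**The concern.** One event has two dispositions, and nothing says which text prevails. Someone who looks up the stopping rule finds an instruction to end study participation, with no pointer to the sections that keep the participant under assessment. There are three recruitment sites, and the PI or a site PI acts on these events, so the rule could be applied differently from site to site.

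The trigger is itself worsening on a PTSD measure. If a site stopped CAPS-5 interviews on the strength of the stopping rule, the missing scores would belong to participants who had just deteriorated. Section 9 does not put the session PCL-5 readings that reveal the deterioration into the missing-data model. A participant with only a baseline CAPS-5 would therefore be treated much like others in the same arm with a similar baseline, which is probably too favourable.

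The two texts also differ on cause. The stopping rule rests on what the participant says. The adverse-event section rests on a determination of relatedness; it names no judge, although the PI or site PI does the questioning. The same participant could meet one test and fail the other.

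**Working it through.** The plan states no figure on this point to reproduce. The check is a comparison of the texts, followed by an illustration of size.

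**Step 1: the texts side by side**

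| Place | Withdrawn from | Later assessments | Judge of cause |
|---|---|---|---|
| Section 10, Stopping Rules | the study | not mentioned | participant |
| Section 11, Managing Adverse Events | study treatment | continue if participant agrees | relatedness determined, judge not named |
| Section 10, Protection against risk, item 4 | study treatment | followed if participant permits | not addressed |
| Section 7, Assessment Schedule | (dropout defined by non-attendance) | all requested | not addressed |
| Section 9 | (dropout for whatever reason) | pursued | not addressed |

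The last four rows agree in direction. The first stands alone, and it is silent on assessments rather than forbidding them.

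**Step 2: which scores are exposed if the stopping rule is applied literally**

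At a weekly pace, session s falls at week s − 1 after the first session.

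- WET: session 5 is at week 4; with the two permitted repeats, session 7 is at week 6. Both precede the first follow-up CAPS-5 at week 10, so a withdrawal during WET could cost all three follow-up scores.
- PE: session 15 is at week 14. A withdrawal before week 10 could cost all three scores; one after the week-10 interview could cost weeks 20 and 30.

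**Step 3: size**

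Inputs from the documents are 90 participants per arm and a margin of 10 CAPS-5 points. Let k be the number in an arm withdrawn with no later CAPS-5, and D the average amount by which their true score exceeds the missing-at-random prediction. Then

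- error in that arm's mean = −k × D / 90
- error in the WET minus PE difference = −(k_WET × D_WET − k_PE × D_PE) / 90

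Equal losses with equal D cancel, so only the net imbalance counts. The documents give neither k nor D. With D assumed to be 10 to 20 points:

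| Net patients | Low (D = 10) | High (D = 20) | Share of margin |
|---|---|---|---|
| 1 | 10/90 = 0.11 | 20/90 = 0.22 | 1.1% to 2.2% |
| 2 | 20/90 = 0.22 | 40/90 = 0.44 | 2.2% to 4.4% |
| 5 | 50/90 = 0.56 | 100/90 = 1.11 | 5.6% to 11.1% |
| 9 (10% of an arm) | 90/90 = 1.00 | 180/90 = 2.00 | 10% to 20% |

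The shift falls in proportion if D is smaller and is zero if D is zero.

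**Step 4: direction**

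A higher CAPS-5 score is worse. Net losses in WET make WET look better and favour non-inferiority; net losses in PE do the reverse. WET's 5 to 7 sessions contain 3 to 5 runs of three consecutive readings, and PE's 8 to 15 sessions contain 6 to 13. If the risk per session were similar, PE would have more withdrawals, which is the conservative direction. The documents give no per-session risk, so the sign stays open.

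**The case against.** The strongest reply is that the plan already keeps these participants. Section 7 defines dropout by attendance, whoever ends treatment, so a participant withdrawn with sessions remaining fits the definition and is asked for every assessment. Section 9 makes no exception by reason. The adverse-event section answers the question for this very trigger. This stands. It makes the stopping rule the outlier and the likely intent clear, but it does not remove the conflicting sentence.

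Four stronger readings are tempting, and the documents do not support them.

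- *Participants who worsen will lose their CAPS-5 data.* That follows only from reading the stopping rule alone.
- *Withdrawal is mandatory in one section and discretionary in the other.* The adverse-event section also says such participants will be withdrawn, and calls the threshold a guide only later. The looseness is mostly within that section.
- *The loss would favour WET.* Step 4 shows that it could go either way, and greater exposure in PE points, if anything, to the conservative side.
- *The bias is material.* Section 11 describes these events as unlikely, and the stopping rule also requires the participant to attribute the rise to treatment. Section 11 further cites a report that acute rises during PE were not linked to dropout or poor outcome. That concerns acute rather than sustained rises, but it is a reason not to presume a large D.

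**Conclusion.** The conflict is real and minor. The stopping rule and the adverse-event section disagree on whether the participant leaves the study or only the treatment, and on who judges cause. The rest of the plan sides with continued follow-up, so data loss is a risk only where a site follows the stopping rule to the letter.

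If that happened, the loss would be informative under the missing-at-random analysis. One or two net patients would move the difference by 0.11 to 0.44 points, on the assumed D of 10 to 20. That would matter only if the confidence limit fell close to 10. Larger shifts need event counts that nothing in the documents supports. Correction is still worthwhile, because an operative safety rule should not leave it unclear whether deteriorating participants remain under study assessment.

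**What to change.** - **Section 10, Stopping Rules.** Replace withdrawal from the study with withdrawal from study treatment, and state that the 10-, 20- and 30-week assessments continue unless the participant declines. Allow a staff-safety exception for the aggression trigger.
- **Sections 10 and 11.** Use one criterion for cause in both places: the PI or site PI judges relatedness after asking the participant.
- **Section 9.** Include the session PCL-5 scores as an auxiliary variable in the maximum likelihood or imputation model, so that observed worsening informs the prediction of any missing CAPS-5.

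The cost is a few wording changes and a little extra modelling. No visit or measure is added: the follow-up assessments and session PCL-5 are already scheduled.
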